4.2. Rationale

Optimal clinical management of CA-ARTI is hampered because of diagnostic delays and suboptimal test sensitivity, leading to incorrect or missing aetiological diagnosis, and over-prescription of antibiotics. Diagnostic and antimicrobial stewardship is important to get the optimal patient management.

There is a need to assess the impact of rapid syndromic diagnostic testing in patients with CA-ARTI presenting to Emergency Rooms on clinical decision making related to:

- Hospitalisation yes or no;
- Start antibiotics yes or no;

At the same time, it must be determined whether the decisions guided by the rapid syndromic diagnostic testing results do not compromise patient safety.

5. OBJECTIVES

5.1. Co-primary objective:

To assess the impact of rapid syndromic testing in patients presenting with CA-ARTI in the ER on:

1. Days in hospital within 14 days after study enrolment
2. Days with antibiotic therapy within 14 days after study enrolment
3. Occurrence of adverse outcome within 30 days after study enrolment

5.2. Secondary objectives:

1. To assess the impact of rapid syndromic testing on healthcare utilization.
2. To assess the impact of rapid syndromic testing on quality of life.
3. To quantify the additional diagnostic yield and sensitivity of rapid syndromic testing because of targets not included in standard of care testing.
4. To quantify the impact of rapid syndromic testing on antimicrobial de-escalation and the choice of antibiotics and prescription of antivirals.
5. To quantify the impact of rapid syndromic testing on detection of antibiotic resistance.
6. To assess the impact of rapid syndromic diagnostic testing on patient bed management and/or isolation measures.

5.3. Exploratory objectives:

- Collect comprehensive data on clinical status and laboratory results for development and validation of clinical algorithms.
- To describe the current routine diagnostic and antimicrobial stewardship policy in Europe and identify good practices
- To estimate the impact of rapid syndromic testing on primary and secondary endpoints for subcategories of hospitals with similar routine diagnostic and antimicrobial stewardship programs.

- To explore clinician views and experiences of the use of rapid syndromic diagnostic testing when patients present to emergency departments (qualitative process evaluation by social sciences).

6. STUDY PARAMETERS/ENDPOINTS

6.1. Main study parameter/endpoint

Co-primary study endpoints:

1. Days alive out of hospital (superiority endpoint), within 14 days after study enrolment
2. Days on Therapy (DOT) with antibiotics (superiority endpoint), within 14 days after study enrolment
3. Adverse outcome (non-inferiority safety endpoint)
 - For initially non-admitted patients: any admission or death within 30 days after study enrolment
 - For initially hospitalised patients: i) any readmission, ii) ICU admission \geq 24 hours after hospitalisation, or iii) death within 30 days after study enrolment

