Expected **benefits of the study** are, together with the main objective of reducing hospitalisation rates and antimicrobial use without adverse outcome, the opportunity for improved training, harmonised improvement of existing guidelines (local and European), opportunity to grow the different existing networks, opportunity to improve surveillance because of underreporting or not available diagnostic tests.

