13. STATISTICAL CONSIDERATIONS

13.1. Sample size calculation

Co-primary endpoints used in the study:

1. Days on antibiotic treatment within 14 days (superiority endpoint)
2. Days alive out of the hospital within 14 days (superiority endpoint)
3. Adverse outcome within 30 days (non-inferiority safety endpoint)

Required sample sizes are presented for endpoint 2 and 3. Endpoint 1 is non-limiting due to having an expected smaller standard deviation compared to endpoint 2 and having the same clinically relevant effect size.

The intervention is considered successful if superiority is demonstrated for either or both endpoints 1 and 2 AND non-inferiority is demonstrated for endpoint 3. We use a hierarchical nested design: superiority primary endpoints are tested first. Only if superiority to at least one of the two superiority endpoints is confirmed, the non-inferiority safety endpoint is taken into consideration. To maintain an overall alpha < 0.05, the two superiority endpoints will be tested using a two-sided alpha of 0.025, while the non-inferiority endpoint will be tested using a one-sided alpha of 0.05. The minimal power for the superiority endpoints is set to 0.9 and for the non-inferiority endpoint to 0.95. This is to maintain overall power of the trial, given the hierarchical testing. For 'Adverse outcome' we considered different non-inferiority margins. For 'Days on antibiotic treatment' and 'Days alive out of the hospital' we defined 1 day as a clinically relevant effect size.

The distribution of endpoint 2 is yet unknown for the ARI population. We supported our sample size calculation using data of patients presenting with CAP to Dutch ERs and hospitalised to a non-ICU ward (ClinicalTrials.gov: NCT02604628). The standard deviation (SD) of 'Days alive out of the hospital within 14 days' in this population was 4 days. The theoretical maximum SD with a 14 days follow-up period is 7 (which would be the case if 50% had zero days and 50% had 14 days alive out of the hospital). However, we expect that in the target population the variability for this endpoint will be less than in the CAP population. We varied the SD to assess the impact on

the sample size. We used a standard correction factor of 1.15 for non-normality of the data. (Table 1) Hence for the superiority endpoints a sample size of 457 per arm would be adequate.

Table 1: Sample sizes for Days alive out of the hospital using different assumptions

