13.2. Analysis populations

A statistical analysis plan will be prepared after protocol approval and once site selection process has been initiated.

The main analyses will be performed for the total population

Analyses will be stratified by:

- age groups (i.e. 18-49, 50-65, >65)
- clinical syndrome: exacerbation of chronic pulmonary disease, influenza-like illness, laryngitis/laryngotracheitis (croup), acute bronchitis
- risk factors. Patient groups at risk for developing severe disease are well known, such as the elderly, patients with chronic pulmonary, cardiovascular or metabolic disease or immunocompromised patients. Clinical predictors of severity are also well known. Still,

within risk groups may exist the uncertainty whether to hospitalise and/or to treat and the impact of testing may be assessed.

- Vaccination status. Influenza. Pneumococcal.

The primary analysis will follow the intention-to-treat principle in which groups are compared based on the allocated regimen. In the per protocol analysis we will exclude participants not receiving the test according to the randomised regimen (e.g. randomised to rapid syndromic testing but not receiving the test).

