13.3. Primary study parameter(s)

Descriptive statistics will be produced and tabular summaries will be presented, stratified according to the allocated group (rapid syndromic testing vs. control). Categorical data will be summarized by the number and percentage of patients in each category. Appropriate summary statistics will be used for continuous variables depending on the distributional assumptions. These include measures of central tendency (mean or median) and dispersion (standard deviation or inter-quartile range).

‘Days on antibiotic treatment’ and ‘Days alive out of the hospital’ will be analysed using a linear regression analysis, including as covariates stratification by age groups and predefined risk factors. Upfront we may expect that the assumption of normally distributed residuals is violated, in which case we will determine the confidence interval by bootstrapping.

Adverse outcome will be analysed using Cox proportional hazards regression adjusted for age groups and predefined risk factors. Risk differences and 90% CI will be inferred by comparing the cumulative incidence of failure at day 30 from the Cox model and bootstrapping for the confidence interval. A 90% CI will be used to be compatible with a one-sided alpha of 0.05.

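### Does the antibiotic-days co-primary need a rule for death, given that an early death lowers the count?

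*Combined protocol and SAP*

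**What the plan says.** Section 6.1 lists three co-primary endpoints. Two are tested for superiority: "Days alive out of hospital (superiority endpoint), within 14 days after study enrolment" and "Days on Therapy (DOT) with antibiotics (superiority endpoint), within 14 days after study enrolment". The third, adverse outcome, is tested for non-inferiority and includes death in both strata. For patients sent home it reads "For initially non-admitted patients: any admission or death within 30 days after study enrolment"; for those admitted at first it is readmission, late ICU admission or death, also to day 30.

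Section 5.1 words the antibiotic objective simply as days with antibiotic therapy over 14 days. Section 9.3 gives the direction of benefit: "main objective of reducing hospitalisation rates and antimicrobial use without adverse outcome".

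Section 13.1, which numbers antibiotic days as endpoint 1, sets the success rule: "superiority is demonstrated for either or both endpoints 1 and 2 AND non-inferiority is demonstrated for endpoint 3". Each superiority test uses two-sided alpha 0.025. The non-inferiority test uses one-sided alpha 0.05 and a 5-point margin.

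Section 13.3 says both day counts "will be analysed using a linear regression analysis", with a bootstrap interval if residuals are not normal. Section 13.2 makes the intention-to-treat comparison primary and says "A statistical analysis plan will be prepared after protocol approval". No section states how a death before day 14 is scored for antibiotic days.

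**The concern.** Fewer antibiotic days is the good direction, and a patient who dies stops accruing them. A patient who dies on day 2 has at most 2 calendar days on antibiotics and scores better than a survivor who completes a 7-day course. A patient given no antibiotics who dies scores the same 0 as one who recovers untreated. The sibling endpoint has survival in its name, so the same death would push the two superiority endpoints in opposite directions.

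A win on either superiority endpoint is enough to move on to the safety test, so antibiotic days alone can carry the efficacy claim. The tested strategy may lead to antibiotics being withheld or patients being sent home, so a mortality difference is not an idle possibility. If it occurred, part of an apparent antibiotic saving could be deaths. The trial is open-label, which makes an unstated scoring rule less comfortable.

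**Working it through.** **Plan's own figures.** With z(0.9875) = 2.2414 and z(0.90) = 1.2816:

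- Superiority, SD 4, 1 day, factor 1.15: n = 2 × 4² × (2.2414 + 1.2816)² × 1.15 = 2 × 16 × 12.411 × 1.15 = 456.7, stated as 457 per arm.
- Non-inferiority, 10% incidence, margin 0.05: n = (1.645 + 1.645)² × 2 × 0.10 × 0.90 / 0.05² = 779.2, rounded up to the stated 780. At 5% incidence the result is 411.2, stated as 412.

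Both reproduce.

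**Inputs for the check.** From section 13.1: 1600 patients, so 800 per arm; SD 4 for the companion endpoint, with antibiotic days expected to vary less, so SD 3 is shown too. Assumed, because the documents give no mortality: 1 to 2 points of excess early death in the tested arm, and 0 to 6 antibiotic days removed per death (0 if antibiotics had been withheld).

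**Bias in the mean.** Shift = excess mortality × days removed: from 0 to 0.02 × 6 = 0.12 day.

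**Threshold for a win.** SE = SD × √(2/800) = 0.20 (SD 4) or 0.15 (SD 3). Multiplying by 2.2414 gives 0.448 or 0.336 day. For deaths alone to reach it at 6 days each would take 0.448/6 = 7.5 points (SD 4) or 0.336/6 = 5.6 points (SD 3). Both exceed the 5-point safety margin.

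**False superiority on antibiotic days, no true prescribing effect.** P = Φ(shift/SE − 2.2414). With no excess deaths, P = 1.25%.

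| Excess | Days removed | Shift | SD 4 | SD 3 |
|---|---|---|---|---|
| 1 point | 4 | 0.04 | 2.1% | 2.4% |
| 1 point | 6 | 0.06 | 2.6% | 3.3% |
| 2 points | 4 | 0.08 | 3.3% | 4.4% |
| 2 points | 6 | 0.12 | 5.0% | 7.5% |

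**False trial success.** Non-inferiority must also pass. With 2 points of excess adverse outcome, the chance is Φ((0.05 − 0.02)/SE − 1.645):

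- 10% v 12%: SE = 0.01564, chance 61%.
- 5% v 7%: SE = 0.01186, chance 81%.

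Multiplying, as if the tests were independent, gives at SD 4 2.0–3.1% (10% incidence) or 2.7–4.1% (5% incidence), and at SD 3 2.7–4.5% or 3.6–6.1%. With no excess deaths the figure is 0.0125 × 0.954 = 1.2%. The tests are not independent: the deaths that help the antibiotic count hurt non-inferiority. Simulation at SD 4 (2% control mortality, 2 points excess, 5 days lost per death) lowers the joint figure by about 0.3 to 0.4 of a point.

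**Would a survival-aware check help?** Days alive and antibiotic-free = 14 − antibiotic days − days dead. A death on day 2 leaves 12 dead days, so 2 points of excess move this difference by 0.02 × 12 = 0.24 day against the intervention. A false antibiotic win already needs at least 0.448 day (SD 4) or 0.336 day (SD 3), so the survival-aware difference usually keeps the same sign. Under the same simulation assumptions, requiring agreement in direction blocks about 1–2% of false antibiotic wins at SD 4 and 16–19% at SD 3. Of full false successes it blocks under 1% and about 7–8%.

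**The case for a change.** The strongest case for acting runs as follows. How death is scored belongs to the definition of a co-primary endpoint. The sponsor put survival into one superiority endpoint and left it out of the other. Section 7.1 shows that the sponsor knew the hazard, because it kept hospital days out of the safety endpoint so that benefits could not offset harm. The safety test is an imperfect screen: it passes 61% to 81% of the time with a 2-point excess. It may be weaker still, because a patient who is readmitted and then dies already counts as an adverse outcome. It also does nothing to correct the antibiotic estimate. With 7 days lost per death, the false-win figures at 2 points are larger, at 6.2% (SD 4) and 9.5% (SD 3).

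The textual omission stands, and so does the point that the safety test does not repair the estimate. Sample size is no obstacle either: with survivors at SD 4 and 2–5% mortality, an alive-and-antibiotic-free count has an SD of about 4.1–4.2, and 800 per arm keeps 90% power up to √(800/(2 × 12.411 × 1.15)) = 5.29.

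The rest carries less weight:

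- Losing 7 days per death exceeds what a day-2 death takes from a 7-day course when both days were treated (7 − 2 = 5).
- The planned rate for the whole 30-day composite is 5% to 10%, equal in both arms. A 1 to 2 point excess of early death alone would be 10% to 40% of it.
- Sections 8.2, 8.3 and 10.1 select against early death. Patients with short life expectancy or confirmed lobar pneumonia are excluded, the team must be able to wait for the result, and eligibility is rechecked before randomisation.
- If harm came from withholding antibiotics, few or no antibiotic days would be lost per death, and this bias would largely vanish.
- The contrast between the two endpoints is softer than it looks. No counting formula is given for days alive out of hospital, and section 5.1 words that objective as days in hospital.

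**Conclusion.** No change to the plan is needed. The antibiotic endpoint measures consumption, and for consumption a zero after death is correct rather than an error. Safety is judged separately, on an outcome that includes 30-day death and must also succeed. Under assumed excess early mortality of 1 to 2 points the distortion is 0 to 0.12 day, well below the 0.34 to 0.45 day needed for significance and the 1-day target. Deaths alone could produce a win only with an excess near or above the safety margin.

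A supporting direction check would add almost no protection at SD 4 and little at SD 3. Making days alive and antibiotic-free the co-primary would replace the stated objective with a different one, a choice on which statisticians reasonably differ. What is left is a scoring convention. The literal reading already supplies one, and the statistical analysis plan announced in section 13.2 is the ordinary place to record it and to tabulate 14-day deaths by arm.

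This rests on the mortality and days-lost ranges, which are assumptions, on an SD of 3 to 4 for antibiotic days, and on 800 analysed per arm. A much larger early mortality difference would matter more, but it would also be increasingly likely to fail non-inferiority: at 10% control incidence, the chance of passing is 35% with 3 points of excess adverse outcome and 5% with 5 points.

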10.4. Clinical data set

Inclusion. Check for inclusion and exclusion criteria and randomisation. Informed Consent Form.**Baseline registration and investigations.**

Signs and symptoms at ER and management plan

Participant background

Vaccination

Co-morbidities and chronic medication

Standard of care haematology and biochemistry

EQ-5D-5L questionnaire

Management: Clinical decision after randomisation and initial results

Investigations: respiratory, urine, faeces, blood, SARS-CoV-2, radiology (only when standard of care)

Day 14: symptoms, EQ-5D-5L questionnaire

Day 30: symptoms, EQ-5D-5L questionnaire

Month 3 (if applicable): symptoms, EQ-5D-5L questionnaire

Month 6 (if applicable): symptoms, EQ-5D-5L questionnaire

Outcomes and safety:

Antibiotic treatment

Antiviral and antifungal agents

Hospital course

Device deficiency

(Severe) Adverse Event

Deviation

End of study

Table 1. Visit Schedule

Procedures	Screening	Enrollment	Hospitalization Period ^e	Face to face, on line questionnaire or phone call		Phone call Extended FU	Phone call Extended FU
	Pre- study procedures	Day 1	> Day 1	Day 14	Day 30	3 months ^f	6 months ^f
	Day 1						
Informed consent	X						
Eligibility criteria	X						
Demographics ^a	X						
Baseline assessment ^b	X						
Vaccination status	X						
Comorbidities and chronic medications	X						
Hospital course ^c		X	X ^e				
Microbiological testing ^d		X	X				
Concomitant therapy review	X	X	X ^e	X	X	X ^f	X ^f
Symptoms review and hospitalizations	X	X	X ^e	X	X	X ^f	X ^f
Quality of life questionnaire EQ5D		X		X	X	X ^f	X ^f

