10.5. Baseline and follow-up data for health-economic analysis

Follow up Assessments: Timepoints: Day 1, Day 14 and Day 30. · 3 months and 6 months for patients included in Extended Follow up

Individual patient data will be clustered in four main categories:

patient status prior to consultation (including quality of life assessment), diagnostics (including microbiological diagnostic tests and thoracic imaging), medicines (antibiotics and any other prescribed medication at the ER/admission including several parameters, antibiotic prescription in the previous 14 days) and patient follow-up (quality of life, adherence to treatment, duration of complaints).

Quality of life- (see eCRF completion guidelines on guidance) The EQ-5D (<https://euroqol.org>) contains 5-dimensions ("5D") related to everyday living: mobility, self-care, usual activities, pain/discomfort, and anxiety/depression. Patients rate the problems they have with each of these dimensions on a 5-level scale ("5-L") from 1 (no problems) to 5 (extreme problems). The second part of the EQ-5D-5L asks patients to grade their current global health status from 0 (worst health you can imagine) to 100 (best health you can image). The questionnaire form takes ± 5-10 min to administer. It needs to be completed by patient or person who has known the patient for > 5 years. (Order of preference: caregiver > spouse > children 18+ > sibling > other acquaintance). For patient questionnaires, patients will receive a link per email to complete the questionnaires online, which will directly be incorporated into the eCRF and be regarded as source data once digitally completed by the patients. If this is not possible or if patients are seen face to face, questionnaires will be completed per paper (source data) and entered in the eCRF by study staff at the site. In this case paper versions will be stored as source data. The third option to have the questionnaires completed is the use of the Interviewer version in which the study staff will interview the patient and complete the data on the paper form (source data) after which data will be entered in the eCRF.

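### The antibiotic-days co-primary does not say whether long-term prophylaxis or courses begun before enrolment count, and the model does not name baseline antibiotic use, which is already recorded.

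*Combined protocol and SAP*

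**What the plan says.** Section 6.1 gives the endpoint as "Days on Therapy (DOT) with antibiotics (superiority endpoint), within 14 days after study enrolment". Sections 5.1, 13.1 and 13.3 reword it but add no rule on indication, start date or long-term use.

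The entry criteria do not settle the matter. Criterion 2a in 8.2 is met if the team is considering antibiotics, admission or both, so a patient already on an antibiotic can qualify through the admission decision. Section 8.3 excludes cystic fibrosis and a respiratory infection episode in the preceding 14 days. It also lets the investigator exclude for abnormalities that hinder endpoint assessment. It does not mention current or long-term antibiotics. Section 13.2 expects exacerbations of chronic pulmonary disease, and among its risk groups "patients with chronic pulmonary, cardiovascular or metabolic disease or immunocompromised patients".

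The relevant facts are recorded at baseline: "Co-morbidities and chronic medication" in 10.4 and "antibiotic prescription in the previous 14 days" in 10.5. Neither is linked to the co-primary. Randomisation is stratified by centre only (10.2). The regression in 13.3 adjusts for age group and predefined risk factors, and baseline antibiotic use is not named.

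For sample size, 13.1 states that "the two superiority endpoints will be tested using a two-sided alpha of 0.025", that "The minimal power for the superiority endpoints is set to 0.9", and that "we defined 1 day as a clinically relevant effect size". No SD is given for antibiotic days. The endpoint is called non-limiting because its SD is expected to be below that of days alive out of hospital, whose SD in hospitalised pneumonia patients ("in this population was 4 days") is the planning value.

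**The concern.** Section 4.2 frames the antibiotic question as whether to start treatment. A patient on daily prophylaxis that simply continues scores 14 days even if the test leads the physician to withhold treatment for the acute episode. If such days count, the endpoint cannot register the effect in that patient. The patient also sits far from the rest of the distribution.

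Two things are at stake. The first is clarity: in an open-label trial, which 7.1 says needs objectively defined outcomes, sites or analysts could count these days differently. The second is precision: patients fixed at 14 days shrink the mean difference and raise the SD, and a smaller SD is the only ground given for leaving this endpoint out of the sample size calculation.

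**Working it through.** **Inputs from section 13.1:** effect 1 day; two-sided alpha 0.025 (z = 2.2414); power 0.90 (z = 1.2816); planning SD 4; non-normality factor 1.15; 780 per arm from the non-inferiority endpoint, raised to 1600 in total for drop-out.

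**Assumed, because the documents give no figure:** the share f of patients fixed at 14 days; a control mean of 5 days in the other patients (range 4-7), with SD 4 or 3.

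**Step 1: the plan's own figures.** 2 × (4 × (2.2414 + 1.2816) / 1)² × 1.15 = 397.16 × 1.15 = 456.7, so 457 per arm, as stated. The non-inferiority figure of 780 (10% incidence, 5% margin, one-sided alpha 0.05, power 0.95) also reproduces.

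**Step 2: a share f fixed at 14 days in both arms.**

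- Effect = (1 − f) × 1 day.
- Variance = (1 − f) × SD² + f(1 − f) × (14 − mean)², averaged over arm means of 5 and 4, so the squared distance averages (81 + 100)/2 = 90.5.
- Power at 780 = Φ(effect / (overall SD × √(2 / (780/1.15))) − 2.2414).

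For f = 5% and SD 4: variance = 0.95 × 16 + 0.0475 × 90.5 = 15.20 + 4.30 = 19.50, so SD 4.42. The standard error is 4.42 × 0.0543 = 0.240, and power is Φ(0.95/0.240 − 2.24) = 0.96.

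| Share f | Effect (days) | Overall SD (others SD 4) | n per arm for power 0.90 | Power at 780 | Overall SD (others SD 3) | Power at 780 |
|---|---|---|---|---|---|---|
| 0 | 1.00 | 4.00 | 457 | 0.99 | 3.00 | >0.99 |
| 2% | 0.98 | 4.18 | 519 | 0.98 | 3.25 | >0.99 |
| 5% | 0.95 | 4.42 | 617 | 0.96 | 3.58 | >0.99 |
| 10% | 0.90 | 4.75 | 795 | 0.89 | 4.03 | 0.97 |

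With means of 4-7 days in the other patients, power at 780 falls below 0.90 once f exceeds about 8-14% (SD 4) or 13-22% (SD 3). With SD 3, a share of about 8-19% lifts the overall SD above 4.

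**Step 3: courses begun before enrolment.** Suppose, pessimistically, that these cannot be shortened and have 3, 5 or 7 days left, with f = 10-30%, mean 5 and SD 4 in the others. The effect is 0.90-0.70 day, but the overall SD falls to 3.87-3.36, and power at 780 is 0.92-0.98. If the test can stop such a course, as the early discontinuation reported in 9.2 suggests, the effect need not be diluted either.

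**Step 4: adjusting for baseline use.** A covariate that identifies the fixed patients removes the between-group term and leaves a variance of about (1 − f) × 16. The effect remains 1 − f.

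| Share f | Adjusted SD | Variance removed | Power at 780, adjusted |
|---|---|---|---|
| 2% | √15.68 = 3.96 | 1 − 15.68/17.45 = 10% | 0.99 |
| 5% | √15.20 = 3.90 | 1 − 15.20/19.50 = 22% | 0.99 |
| 10% | √14.40 = 3.79 | 1 − 14.40/22.55 = 36% | 0.98 |

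**The case against.** The strongest reply is that the protocol is silent, not wrong. It speaks of therapy and treatment, which can be read as leaving prophylaxis out, and the SAP announced in 13.2 could define the count. That stands: the supportable statement is that the rule is undefined. A reader might infer that the plan counts every antibiotic day, but no section says so.

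A reader might also infer that courses begun before enrolment are fixed near the ceiling. They are not. They may have few days left, and de-escalation is a stated objective (5.2). Step 3 shows no rise in variance even if they cannot be shortened.

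A third inference is a serious power loss. At 457 per arm the SD 4 case would give power of 0.86, 0.79 and 0.67 for shares of 2%, 5% and 10%. The trial is not that size: non-inferiority requires 780 per arm and about 800 are to be randomised. SD 4 is also the hospital-days value, and 13.1 expects less for antibiotic days.

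Finally, total antibiotic exposure is a defensible endpoint, since 9.3 names reduced antimicrobial use as an aim. Redefining the primary count is therefore a debatable choice. Dropping only agents that were continued unchanged would be worse, because that is known only after randomisation and can depend on the test result.

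What remains is that the counting rule is unstated, the entry limits are partial, and recorded baseline data that would recover precision are not named in the model.

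**Conclusion.** The point holds as an undefined counting rule and an avoidable loss of precision. It is not bias between arms: randomisation balances these patients in expectation. Under the assumed mean of 5 and SD 4, the loss at 780 per arm is slight at a 2% share (power 0.98 against 0.99), modest at 5% (0.96) and just below the 0.90 target at 10% (0.89). With SD 3 it does not go below about 0.97 at those shares. The dilution and added variance apply to continuous prophylaxis only. The size depends on a share that the documents do not give. The claim that this endpoint is non-limiting is not refuted, but it rests on an SD for which no figure is offered.

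**What to change.** In 13.3, add to the antibiotic-days regression a pre-randomisation covariate for antibiotic use at presentation, with three levels: none, current short course, long-term prophylaxis. Derive it from the chronic-medication record (10.4) and the record of antibiotics in the previous 14 days (10.5), both fixed before allocation is known. All randomised patients stay in, and the all-antibiotic endpoint is unchanged. State in 6.1 that this all-antibiotic count is what is meant.

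As a sensitivity analysis, repeat the count leaving out agents recorded before randomisation as long-term treatment. Identify them from the baseline record alone, with no condition on what happened to them afterwards.

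The cost is one clarifying sentence, one covariate and one extra analysis, with no new data. Under the assumptions above the covariate brings the SD to about 3.8-4.0 and power at 780 to about 0.98-0.99. It does not undo the dilution: the estimate remains the average over all patients, including those on prophylaxis. The sensitivity count shows how far that matters.
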